1.4. Prader-Willi Syndrome

Prader-Willi Syndrome (PWS), first described in 1956, is a multifaceted developmental disorder and the most common genetic syndrome associated with obesity (Gunay-Aygun et al., 1997; McAllister and Whittington, 2011). It is caused by the absent expression of paternally-inherited genes in the PWS region on 15q11-q13 (Ledbetter et al., 1981). While it presents with generalized hypotonia and developmental delay in infancy, PWS then manifests with uncontrollable appetite, hyperphagia, and excessive weight gain leading to severe obesity (Grechi et al., 2012).

Clinically, PWS patients suffer a complex pattern of physical, behavioral, endocrine, and intellectual deficiencies. Endocrine abnormalities lead to hypogonadism and short stature. In particular, growth hormone deficiency is reported to occur in 40% to 100% of the population (Griggs et al., 2015) and is commonly treated with growth hormone (Angulo et al., 2015). Behavioral disorders include obsessive compulsive behaviors such as skin picking, hoarding, re-doing, and repetitive speech (Griggs et al., 2015).

However, it is the appetite behavior classified as hyperphagia in Prader-Willi Syndrome that is the most life threatening (Dykens et al., 2007; Griggs et al., 2015) and until recently, no patient lived over the age of 50 due to morbid obesity and its related complications (Aycan et al., 2014). The mortality rate in patients with PWS is six times higher than patients with other intellectual disabilities (Einfeld and Kavanagh, 2006) and mortality in patients not treated with growth hormone was estimated to be 3% per year between the ages of 6 and 56 compared to the general population mortality of 0.13% below 55 years. Mortality in Prader-Willi Syndrome below 5 years of age has not been determined (Eiholzer, 2005).

Hyperphagic behaviors can also be dangerous in persons who are not obese, with increased risks of death due to choking while sneaking food, and gastric perforations after consuming more food than usual (Dykens et al., 2007). Approximately 8% of deaths in individuals with PWS are reported due to the choking, especially on hot dogs (Stevenson et al., 2007). PWS patients also are known to eat discarded (contaminated) food and items that are not for human consumption such as pet food, or even non-food items such as paint or paper (Griggs et al., 2015).

Currently, there are no FDA-approved therapies for the treatment of hyperphagia or obesity in patients with PWS. In addition, drugs that have demonstrated efficacy in the past have been withdrawn or have significant safety concerns (e.g., rimonabant, beloranib). Therapy consists mostly of strict and consistent behavioral controls surrounding eating that prevent independent living for adult patients. Recent studies investigating modulation of the endocannabinoid system, however, have shown promise.

The endocannabinoid system appears to be critically involved in the regulation of appetite, body weight, metabolism, hypothalamic-pituitary-adrenal axis, and reward brain circuitry (Liu et al., 2005; Edwards and Abizaid, 2016). Endocannabinoid receptor CB1, is widely expressed in the central nervous system, autonomic gastric vagus nerve endings of the peripheral nervous system, and other key cells involved in body energy metabolism, including adipocytes, hepatocytes, and myocytes (Bensaid et al., 2003; Liu et al., 2005; Osei-Hyiaman et al., 2008). In clinical studies, compounds with endocannabinoid effects (fenfluramine, rimonabant) have shown significant effects on weight and appetite suppression (Pinder et al., 1975; Despres et al., 2005; Pi-Sunyer et al., 2006). These effects on appetite also occurred in 19% of epilepsy patients treated with

Epidiolex[®] (i.e., cannabidiol extracted from the cannabis plant) during an open-access program for patients with pediatric seizure disorder (Devinsky et al., 2016). Because of the well-characterized orexigenic activity of THC (a strong CB1 agonist), the CB1 antagonist, rimonabant, was studied and found to be effective in treating obesity in adults without PWS (Pi-Sunyer et al., 2006). Both fenfluramine and rimonabant were subsequently withdrawn from the market, however, due to unacceptable side effects (McCann et al., 1997).

CBD is a low-affinity antagonist of CB1, but it may also modulate CB1 receptor signaling through its inhibition of the metabolism of the endogenous cannabinoid, anandamide (Ibeas Bih et al., 2015; Laprairie et al., 2015). As for appetite, CBD has been shown to decrease food intake in rats under stressful conditions and reduce *ad lib* intake of high-sugar feed when compared to vehicle-treated controls (Silveira Filho and Tufik, 1980). In addition, CBD has been shown to diminish daily food consumption without affecting daily water intake (Wierucka-Rybak et al., 2014) as well as inhibited hyperphagia induced by CB1 receptor or 5-hydroxytryptamine (5-HT_{1A}) serotonin receptor agonists suggesting a role for CBD as a regulator of food intake. Perhaps just as importantly, CBD decreases cue-induced craving and reduces the reward induced by drugs of abuse by modulating the cholinergic-dopaminergic pathway that may drive such behaviors in PWS patients (Von Deneen et al., 2009; Hurd et al., 2015; Parsons and Hurd, 2015).

Thus, CBD may have potential to address the main medical problems associated with Prader-Willi Syndrome patients leading to obesity and related mortality. Insys Development Company, Inc. (Insys) is manufacturing a pharmaceutical grade synthetic cannabidiol formulation (Cannabidiol Oral Solution) to be advanced into clinical development for the treatment of hyperphagia behaviors and obesity in patients with Prader-Willi Syndrome.

1.5. Dose Selection Rationale

Doses up to 40 mg/kg/day were administered in the Phase 1/2 PK study (Protocol INS011-14-029) and the long-term safety study (Protocol INS011-14-030). The maximum dose given was 3200 mg/day in an adolescent. These doses were generally well tolerated even without titration. Because the Prader-Willi patients enrolled in this study will be obese and there were concerns that distribution to fat would decrease the effective dose in these subjects, the maximum tolerated dose identified in the previous PK and safety study will be given. To maximize tolerability, a one-week titration period is included in this study (initial dose of 20 mg/kg/day for 3 days, followed by 30 mg/kg/day for 3 days, and then 40 mg/kg/day starting on Day 7 and continuing through the duration of the study).

1.6. Summary of Potential Risks and Benefits

As reviewed in Sections 1.2 and 1.3, numerous nonclinical and clinical studies have examined other formulations of CBD. Several areas of potential concern have been identified with the use of CBD, especially in nonclinical studies. These include:

- Competitive binding of CYP proteins (thus, an impact on drug metabolism in the liver). Cannabidiol is metabolized predominantly by CYP3A4 and CYP 2C19. Cannabidiol may inhibit these two isozymes, as well as having small effects on CYP3A5, CYP2D6, CYP1A1, and CYP2C9.
- Potential downregulation of immune responses involving the T, B, T-helper, and T cytotoxic subsets of leukocytes and/or those dependent on IL-2 or IFN- γ .

Based on recent studies of cannabinoid administration in humans, controlled CBD may be safe in humans and animals. While further studies are needed to clarify these reported *in vitro* and *in vivo* side-effects (Braut-Boucher et al., 1986), no infection-related events have been reported in recent studies in the pediatric seizure population.

The inclusion/exclusion criteria, concomitant medication guidelines, and safety monitoring (AEs, clinical laboratory, vital signs, ECG, and physical examination assessments) planned for this study are intended to minimize these potential safety risks.

Criteria for removal of subjects from the study and stopping rules will dictate discontinuation of subject participation should a safety issue arise (see [Section 3.3](#) and [Section 3.6](#), respectively).

The appetite behavior classified as hyperphagia in Prader-Willi Syndrome is the most life threatening (Dykens et al., 2007; Griggs et al., 2015) and until recently, no patient lived over the age of 50 years due to morbid obesity and the related complications (Aycan et al., 2014). The mortality rate in patients with PWS is six times higher than patients with other intellectual disabilities (Einfeld et al., 2006) and mortality in patients not treated with growth hormone was estimated to be 3% per year between the ages of 6 and 56 years compared to the general population mortality of 0.13% below 55 years; mortality in Prader-Willi Syndrome below 5 years of age has not been determined (Eiholzer, 2005).

Hyperphagic behaviors can also be dangerous in persons who are not obese, with increased risks of death due to choking while sneaking food, and gastric perforations after consuming more food than usual (Dykens et al., 2007). Approximately 8% of deaths in individuals with PWS was reported due to the choking, especially on hot dogs (Stevenson et al., 2007). Prader-Willi Syndrome patients also are known to eat discarded (contaminated) food and items that are not for human consumption such as pet food, or even non-food items such as paint or paper (Griggs et al., 2015).

Subjects with PWS continue to experience a significant unmet medical need, especially when it comes to hyperphagia behavior and obesity. There are no approved drugs currently to treat these behaviors. Fenfluramine demonstrated significant efficacy in Prader-Willi Syndrome patients but was removed from the market due to cardiac valve concerns. Rimonabant was approved in the EU for obesity and a trial was ongoing in Prader-Willi Syndrome. However, the drug was never approved in the US and removed from the market in the EU due to significant psychiatric side effects. A trial in PWS, while demonstrating a trend for efficacy was terminated early for safety concerns. Currently, Zafgen's product Beloranib demonstrated significant positive effects on weight loss and hyperphagia behavior in patients with Prader-Willi syndrome but is currently on hold due to two deaths that were thought to be caused by thrombotic events. Orlistat, lorcaserin, Qsymia, and Contrave have been approved for obesity but not studied in the Prader-Willi Syndrome population. Therefore, there continues to be a high unmet need for an efficacious and safe treatment for this population.

Cannabidiol has been safely administered to over 300 medically complex children and was generally well-tolerated. The adverse events recorded do not correspond to those encountered by previous trials in patients with Prader-Willi syndrome. The anxiolytic effects of CBD and its indirect effect on the CB1 receptor suggest an improved side effect profile in this population.

In conclusion, there is both pre-clinical and clinical evidence that affecting the endocannabinoid system with cannabidiols, including cannabidiol, may demonstrate a clinically relevant effect on

the hyperphagia behaviors as well as lead to weight loss in patients with Prader-Willi Syndrome. Insys believes that due to the safety and tolerability of cannabidiol demonstrated by the data available in the literature and collected by the sponsor, and the life-threatening obesity in Prader-Willi Syndrome, the demonstration of efficacy and safety of Cannabidiol Oral Solution in this population will be a valuable option to treat these patients.

2. STUDY OBJECTIVES

2.1. Primary Objective

The primary objective of this study is:

- To assess the efficacy of Cannabidiol Oral Solution on hyperphagia-related behavior in patients with Prader-Willi Syndrome (PWS) as measured by total score of the Hyperphagia Questionnaire for Clinical Trials (HQ-CT).

2.2. Secondary Objectives

The secondary objectives of this study are:

- To assess the efficacy of Cannabidiol Oral Solution on the change in total body weight in patients with PWS.
- To assess the responder rate (responder is defined as 6-point decrease on the HQ-CT from Baseline to End of Study).
- To assess the efficacy of Cannabidiol Oral Solution by measuring the changes in Patient Global Impression of Change (PGI-C).
- To assess the safety and tolerability of Cannabidiol Oral Solution in patients with PWS.
- To assess the efficacy of Cannabidiol Oral Solution on eating behavior in patients with PWS as measured by the Three Factor Eating Questionnaire -18-item version (TFEQ-R18).
- To assess the impact on Quality of Life in patients with PWS as measured by the PROMIS Life Satisfaction and Positive Affect pediatric short-form questionnaires.
- To assess the impact on physical activity in patients with PWS as measured by the PROMIS Physical Activity and Fatigue questionnaires.

2.3. Exploratory Objective

The exploratory objective of this study is:

- To assess the efficacy of Cannabidiol Oral Solution on body composition and bone mineral density, as measured by dual-energy X-ray absorptiometry (DEXA).

3. INVESTIGATIONAL PLAN

3.1. Overall Study Design

This is a double-blind, randomized, placebo-controlled, Phase 2 clinical trial in patients diagnosed with Prader-Willi Syndrome. Patients will receive either Cannabidiol Oral Solution (40 mg/kg/day) or placebo with patients randomized in a 1:1 ratio. Randomization will be stratified according to use of growth hormone treatment.

Approximately 66 male and female patients aged 8 to 17 years, inclusive, with a genetically confirmed diagnosis of Prader-Willi Syndrome will be enrolled in the study.

The study will consist of the following six periods:

- Screening Period (2 weeks)
- Placebo Lead-In Period (2 weeks)
- Titration Period (1 week)
- Maintenance Period (12 weeks)
- Taper Period (1 week)
- Follow-Up Period (1 week)

Patients who meet entry criteria will be assigned to a 2-week single-blind Placebo Lead-In Period. Following the placebo single-blind lead-in period, patients will be randomly assigned to receive double-blind treatment with either Cannabidiol Oral Solution treatment at a dose of 40 mg/kg/day or matching placebo divided twice daily with standard meal (a 1-week Titration Period followed by a 12-week Maintenance Period). During the Titration Period, Cannabidiol Oral Solution will be titrated as follows: Days 1-3: 20 mg/kg/day, Days 4-6: 30 mg/kg/day, Day 7: 40 mg/kg/day. The Investigator or designee will call on Day 3 and Day 6 to determine if the patient's dose may be titrated to the next dose level. If the Investigator determines that the patient is unable to tolerate the higher dose, the patient should be withdrawn from the study.

[figure not shown]
During the Maintenance Period, patients may have their dose of blinded study medication adjusted down to 30 mg/kg/day at the discretion of the Investigator or qualified designee based on the patient's tolerability.

After completion of the study, patients will be offered an opportunity to enroll into an open-label, long-term safety study. Patients who do not elect to enroll in the long-term safety study will be titrated off the study drug over 7 days according to the following schedule: 40 mg/kg/day to 30 mg/kg/day for 3 days, to 20 mg/kg/day for 3 days, and then discontinue the drug on Day 7. A final safety follow-up phone call will be placed 2 weeks after study completion (Visit 10) for patients who do not elect to continue into the long-term safety study and whose AEs have not resolved prior to the last visit.

The study design and patient progression through the study is outlined in [Figure 1](#).

All screening, efficacy, and safety evaluations will be performed according to the schedule of assessments summarized in [Table 1](#).

Figure 1: Study Design Schematic

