- Placebo Lead-In Period (2 weeks)
- Titration Period (1 week)
- Maintenance Period (12 weeks)
- Taper Period (1 week)
- Follow-Up Period (1 week)

Patients who meet entry criteria will be assigned to a 2-week single-blind Placebo Lead-In Period. Following the placebo single-blind lead-in period, patients will be randomly assigned to receive double-blind treatment with either Cannabidiol Oral Solution treatment at a dose of 40 mg/kg/day or matching placebo divided twice daily with standard meal (a 1-week Titration Period followed by a 12-week Maintenance Period). During the Titration Period, Cannabidiol Oral Solution will be titrated as follows: Days 1-3: 20 mg/kg/day, Days 4-6: 30 mg/kg/day, Day 7: 40 mg/kg/day. The Investigator or designee will call on Day 3 and Day 6 to determine if the patient's dose may be titrated to the next dose level. If the Investigator determines that the patient is unable to tolerate the higher dose, the patient should be withdrawn from the study.

During the Maintenance Period, patients may have their dose of blinded study medication adjusted down to 30 mg/kg/day at the discretion of the Investigator or qualified designee based on the patient's tolerability.

After completion of the study, patients will be offered the opportunity to enroll in an open-label, long-term safety study. Patients who do not elect to enroll in the long-term safety study will be tapered off the study drug over 7 days according to the following schedule: 40 mg/kg/day to 30 mg/kg/day for 3 days, 30 mg/kg/day to 20 mg/kg/day for 3 days, discontinuing the drug on Day 7. A final safety follow-up will be conducted 2 weeks after study completion (Visit 10) for patients who do not elect to continue into the long-term safety study.

Safety assessments for all patients will include medical history, physical examination, vital signs (seated blood pressure, pulse rate, temperature, and respiration rate), clinical laboratory testing (including a CBC test), 12-lead ECG, urine drug screen (including THC), prior medication history, concomitant medication, and AE assessments.

Blood draws for PK sampling will be taken prior to medication dosing at specific study visits for determination of the plasma levels of CBD and 7-OH-CBD.

Number of patients (planned):

Approximately 66 male and female patients will be enrolled to have 60 patients (30 patients per treatment group) complete the study.

Diagnosis and main criteria for inclusion:

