			TITRATION PERIOD ^a (1 Week)			MAINTENANCE PERIOD (12 Weeks)						
Visit Number	1	2	3 Baseline	Call/ Email	4	5	6	7	8	9	10 Study Completion / Early Withdrawal	11
Study Time Point	Week -4 to -2	Week -2	Day 1	Day 3 & 6	Day 7	Week 3	Week 5	Week 7	Week 9	Week 11	Week 13	Week 15
Visit Window (Days)	±3	±3	±3	0	0	±3	±3	±3	±3	±3	±3	±3
PROMIS Physical Activity and Fatigue pediatric short-form questionnaires			X			X			X		X	
Patient Global Impression of Severity (PGI-S)			X									
Patient Global Impression of Change (PGI-C)						X			X		X	
DEXA scan ^c			X								X	
Columbia Suicide Severity Rating Scale (C-SSRS)			X								X	
Review of concomitant medications	X	X	X	X	X	X	X	X	X	X	X	X
Review of adverse events	X	X	X	X	X	X	X	X	X	X	X	X
Pharmacokinetics ^c			X				X		X		X	

DEXA = Dual energy X-ray absorptiometry; PROMIS = Patient-Reported Outcomes Measurement Information System

^a Titration schedule = Days 1-3: 20 mg/kg/day; Days 4-6: 30 mg/kg/day; Day 7: 40 mg/kg/day. Phone calls will be made at Day 3 and Day 6 to determine if the patient’s dose may be titrated to the next dose level.

^b The Follow-up Visit is only for patients who do not choose to enroll in the long-term safety study and are tapering off the study drug. Patients will return to the site for assessment of concomitant medications, AEs, and to return and reconcile study drug.

^c Blood draws for trough pharmacokinetic analyses of CBD and metabolite 7-OH-CBD will be collected prior to morning dose at Visit 3 (Baseline) and Visit 6, 8, and 10 during the Maintenance Period.

^d Blood and urine samples for hematology, chemistry, and urinalysis will be collected at Screening (visit1), and Study Completion (Visit 10)/Early Withdrawal. Blood sample for complete blood count (CBC) will be collected at Week 3 (Visit 5).

^e DEXA scan will be completed on a subset of 20 patients.

TABLE OF CONTENTS

PROTOCOL APPROVAL PAGE	2
PROTOCOL SYNOPSIS	3
TABLE OF CONTENTS.....	14
LIST OF TABLES	19
LIST OF FIGURES	19
LIST OF ABBREVIATIONS AND DEFINITIONS OF TERMS.....	20
1. INTRODUCTION	23
1.1. Cannabidiol.....	23
1.1.1. Mechanism of Action	24
1.1.2. Metabolism and Potential Drug Interactions	24
1.2. Nonclinical Experience.....	24
1.2.1. Safety	24
1.2.2. Efficacy.....	25
1.2.2.1. Single Dose Regimens	25
1.2.2.2. Multiple Dose Regimens	26
1.3. Clinical Experience.....	26
1.3.1. Pharmacokinetics	28
1.3.2. Overview of Safety	29
1.3.3. Clinical Safety Data.....	29
1.4. Prader-Willi Syndrome.....	32

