4.1.5. Taper Period

Following the completion of the Maintenance Period (Visit 10), patients will have the option to continue treatment in an open-label long-term safety study. Patients who choose to enroll in the long-term safety study will not have a follow-up visit. Patients who do not choose to enroll in the long-term safety study will taper the dose of study medication according to the following schedule: 40 mg/kg/day dose will be reduced to 30 mg/kg/day for three days, then 30 mg/kg/day will be reduced to 20 mg/kg/day for three days and then discontinued; 30 mg/kg/day dose will be reduced to 20 mg/kg/day for three days and then discontinued.

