4.1.6. Follow-Up Period

A follow-up visit call will occur within 2 weeks after study completion. No study medication will be provided during this time.

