4.8. Treatment After End of Study

After completion of the study, patients will be offered the chance to enroll into an open-label, long-term safety study. Patients who choose to enroll in the long-term safety study will not have a follow-up visit. Patients who do not choose to enroll in the long-term safety study will be tapered off study medication and complete a follow-up visit approximately 2 weeks after study completion.

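### Protocol 3.1 limits the final safety contact to patients with unresolved adverse events, while the visit schedule gives Visit 11 to every patient who does not roll over (minor)

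*Protocol*

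**What the plan says.** After Visit 10 (Week 13) a patient either rolls over, since "patients will have the option to continue treatment in an open-label long-term safety study" (Protocol 4.1.5), or tapers off and is followed up once. The documents describe that one follow-up contact in several ways.

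- **Protocol 3.1**: a telephone call two weeks after Visit 10, for non-rollover patients "whose AEs have not resolved prior to the last visit".
- **Protocol synopsis**: "A final safety follow-up will be conducted 2 weeks after study completion (Visit 10) for patients who do not elect to continue". It sets no adverse event condition and states no mode.
- **Protocol Table 1, footnote b**: "Patients will return to the site for assessment of concomitant medications, AEs, and to return and reconcile study drug". The footnote covers non-rollover patients who are tapering.
- **Protocol 4.1.6**: "A follow-up visit call will occur within 2 weeks after study completion". It names no population.
- **Protocol 4.8**: non-rollover patients "will be tapered off study medication and complete a follow-up visit approximately 2 weeks after study completion".
- **Protocol 7.6.1**: Visit 11 at Week 15 for non-rollover patients, with drug collection, concomitant medications and adverse event review.
- **SAP 2.2**: a telephone call for non-rollover patients, otherwise close to the 3.1 sentence but without the adverse event clause.
- **SAP Appendix A, footnote b**: the same text as Table 1 footnote b.

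Protocol 3.1 also contains a general pointer to Table 1: "All screening, efficacy, and safety evaluations will be performed according to the schedule of assessments summarized in" that table.

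On analysis, SAP 7.7.2 counts an event as treatment-emergent if it starts up to 14 days after the last double-blind dose, and the partial-date rule in SAP 6.2 uses the same end. Neither mentions the first open-label dose.

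**The concern.** The clause in 3.1 selects patients by the events they already have at Visit 10. A post-taper contact exists largely to find events that start later, and those cannot be open at Visit 10. Protocol 6.2.6.8 does not fill the gap: it says how long known events are followed, not how new ones are found. Read literally, 3.1 would leave new-onset events after Visit 10 without a scheduled review in the patients who reached Visit 10 with no open event. Safety and tolerability is a secondary objective, and the patients are aged 8 to 17.

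The mode matters for a practical reason. Footnote b and 7.6.1 require study drug to be returned and reconciled at this contact, and Protocol 5.2 treats the product as a Schedule I substance. A telephone call does not provide for that. The SAP also disagrees with itself: a call in 2.2, a return to site in Appendix A.

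**Working it through.** No figure in the plan depends on this point, so the check is a comparison of texts followed by day arithmetic.

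**Step 1. The statements side by side.**

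| Place | Population | Adverse event condition | Mode |
|---|---|---|---|
| Protocol 3.1 | Non-rollover | Yes | Call |
| Protocol synopsis | Non-rollover | None | Not stated |
| Protocol Table 1, note b | Non-rollover, tapering | None | Return to site |
| Protocol 4.1.6 | Not stated | None | Visit and call combined |
| Protocol 4.8 | Non-rollover | None | Visit |
| Protocol 7.6.1 | Non-rollover | None | Visit 11, with drug collection |
| SAP 2.2 | Non-rollover | None | Call |
| SAP Appendix A, note b | As Table 1 | None | Return to site |

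One place carries the condition and seven do not. The seven are not independent: Appendix A reproduces Table 1, and 4.1.6 names no population, so its silence says little. That leaves 7 − 2 = 5 separate statements (synopsis, Table 1, 4.8, 7.6.1, SAP 2.2) that define the population without the condition.

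**Step 2. Timing of the contact.** Inputs: Visit 10 at Week 13 and Visit 11 at Week 15 (Table 1).

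- Nominal gap: (15 − 13) × 7 = 14 days.
- If the ±3-day window is counted from the actual Visit 10 (an assumption; the anchor is not stated): 14 − 3 = 11 to 14 + 3 = 17 days.

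**Step 3. Position relative to the taper.** From 40 mg/kg/day the taper is 3 days at 30 and 3 days at 20 (Protocol 4.1.5). From the reduced dose, "30 mg/kg/day dose will be reduced to 20 mg/kg/day for three days and then discontinued". Take Visit 10 as day 0.

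- From 40 mg/kg/day: 3 + 3 = 6 dosing days; Visit 11 is 14 − 6 = 8 days after the last taper dose.
- From 30 mg/kg/day: 3 dosing days; Visit 11 is 14 − 3 = 11 days after the last taper dose.

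Visit 11 is therefore a post-taper review. Table 1 has no contact between Visit 10 and Visit 11.

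**Step 4. Position relative to the SAP window.** If taper doses count as double-blind doses, the treatment-emergent window ends at day 6 + 14 = 20 or day 3 + 14 = 17. If they do not, it ends at day 14. In each case the target day of Visit 11 falls within the window, and Visit 11 is the only adverse event review that this study schedules after Visit 10. Under the 3.1 clause, patients with no open event at Visit 10 would have no scheduled collection in that part of the window.

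**Step 5. Rollover patients.** With the last double-blind dose at Visit 10, the window runs to day 14. If open-label dosing starts at once (an assumption; the start date is not given), up to 14 open-label days fall inside it. SAP 5.2 analyses Safety patients by the treatment they actually received. An open-label event of a former placebo patient that was recorded on this eCRF in those days would then appear under placebo.

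**The case against.** The strongest reply is that the protocol already settles the matter. The paragraph on evaluations in 3.1 defers to Table 1, section 7 does the same, and Table 1 and 7.6.1 schedule Visit 11 for non-rollover patients. Adverse events are recorded throughout the study (6.2.6.7), and drug must be accounted for (5.3), which brings tapering patients back. Harm would require a site to follow one narrative clause over the schedule. This stands, and it is why the point is minor. It does not remove the conflict: 3.1 is operative text, and a site or monitor still has to choose between it and 7.6.1.

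Four stronger readings are tempting, and the documents do not support them.

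- A reader might infer that the clause removes adverse event contact during the taper. No version plans a contact there; at most one post-taper review is lost.
- A reader might infer that the SAP's 14-day lag contradicts Protocol 8.6.4.1, which ties treatment-emergent events to the treatment period. Section 8 leaves detailed conventions to the SAP, and a lag is a reasonable way to make that definition operational and to catch post-taper events.
- A reader might infer that open-label events will be counted under placebo. SAP 7.7.2 classifies only events on this study's eCRF, rollover patients have no Visit 11, and no routine route for their later events into this database is described.
- A reader might extend the correction to Protocol 9.5, which also mentions a telephone follow-up call. That section governs termination by the sponsor and covers all patients then participating, so changing it would alter a separate provision.

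**Conclusion.** The inconsistency is real. The AE restriction in 3.1 conflicts with five separate statements of the same contact, and the mode of contact is not settled in either document. What is at stake is one scheduled adverse event review per affected patient, nominally 14 days after Visit 10 and 8 or 11 days after the last taper dose. How many patients or events would be affected cannot be derived: it depends on how many decline the open-label study, how many of those have no open event at Visit 10, and how many sites follow the clause rather than Table 1. The day counts describe the period concerned, not a size of bias. Safety analyses are descriptive and the efficacy analyses are unaffected.

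The absence of an open-label cut in the treatment-emergent window is true on the text, but no error follows from it. Its effect depends on the open-label start date and on recording rules that these documents do not give. It supports an optional safeguard only.

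**What to change.** 1. In Protocol 3.1, delete the condition "whose AEs have not resolved prior to the last visit" together with the conjunction that introduces it.
2. In Protocol 3.1, Protocol 4.1.6 and SAP 2.2, replace the call wording with the Visit 11 site visit of Table 1 and SAP Appendix A, for all patients who do not roll over. Leave Protocol 9.5 as it is.
3. Optional: in SAP 7.7.2 and 6.2, end the treatment-emergent window at the earlier of 14 days after the last double-blind dose or the first open-label dose. List any later events and flag them as having open-label onset.

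The cost is protocol and SAP wording. Visit 11 is already scheduled, so no assessment is added, and neither the sample size nor any efficacy analysis changes. The optional item needs the first open-label dose date to be available to the programmer.
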